Inclusion Screener*	X			
Communication and SCD Pain Knowledge measure**		X	X	X
Pain Assessment Tool		X	X	X
SCD Transition Program Questionnaire		X	X	X
SCD Transition Knowledge Questionnaire		X	X	X
Sickle Cell Self-efficacy Scale		X	X	X
Family Cohesion Scale		X	X	X
CDC Flu IQ Questionnaire		X	X	X
App Usage			X	X
System Usability Scale			X	X

* Completed by parent only

** Completed by teen and parent

referred to their treating physician immediately. Based on our experience and demonstrated ability to conduct this type of research, we are confident we can achieve safe intervention delivery.

3C.8. Data Collection, Management, and Security. KB has used online data collection successfully in a number of studies. Study consents and pretests and posttests will be collected online via participants' personal smartphone or tablet. Surveys will be programmed using QuestionPro software on KB's secure web server to ensure a structured approach and reduce errors/missing values. All procedures will be approved by KB's IRB.

KB has considerable experience maintaining large databases and ensuring high-quality data. [name], KB's Biostatistical Manager, will supervise data management. All data will be uploaded in real-time using KB's secured network; data will be de-identified and stored in KB's secured database. Established KB protocols for quality assurance (valid ranges; internal consistency checks, etc.) will ensure high quality data. The KB data team will compile master data files. Survey and app usage data will be linked. Missing data should be limited since data is recorded electronically. Staff will identify missing responses and check that entries were not intentionally skipped. Analyses will be done on data collected. While unlikely, data may not be missing at random (NMAR). KB will assign all lost responses to extreme category and perform multiple imputation procedures that can handle various amounts of missing data and use covariates and propensity scores.

Data security: KB's server farm has 5 Dell PowerEdge servers with two 3.2 Ghz Xeon processors, four with 32 gigabytes of RAM and one with 64 gigabytes, and three 1 Terabyte hard drives that operate off a hardware RAID5 system, connected to a local area network (LAN) running the Windows 2008 or 2012 operating system and to the Internet through a 20-megabyte Fiber connection. KB programmers monitor and maintain all programs and databases. Sensitive information is protected by a hardware firewall (Cisco ASA 5505) and each server has its own native Windows security software. All KB servers are connected via 1 Gigabit high-speed switched network, ensuring high-speed transfer between machines. All networked computers are protected from viruses by Sunbelt Vipre Enterprise. Nightly backup of each computer protects against data loss.

C.10. Evidence for Scientific Rigor and Potential Limitations. The study has numerous strengths, few limitations, and is scientifically rigorous. The study is theory-driven (i.e., User-centered Design and Social Cognitive theories). Formative data will incorporate multiple stakeholder input. The programming approach will be multi-model and evidence-based (i.e., ADDIE Model, MDA framework, AGILE programming) resulting in a systematic, flexible, and cost-effective approach. Sample sizes are sufficient and supported by the literature. Effectiveness will be evaluated in a within-subjects design which allows for sufficient power (i.e., statistical inference with fewer subjects), efficiency (i.e., quicker trial completion), and longitudinal analysis (i.e., individual changes over time). The study team and environment are strong. Potential limitations are: (1) difficulty recruiting; (2) sources of bias; and (3) lack of control group. We have tried to reduce their impact. We will work closely with the EAB and PAB to maximize recruitment. Our primary outcome measure is new, but we are using a rigorous approach to scale development. Self-report instruments are open to bias, however the use of validated measures are a strength. Limitations of no control group are lessened via the use of a time-series design for outcome changes and use of a nonequivalent dependent variable.

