3C.5. Experimental Design (AIM 3). AIM 3 will test the full *Pinpoint* app with 13-17 year olds with SCD (n=100) using a within-subjects times series design over 12 weeks to evaluate changes in (1) knowledge acquisition for communicating about pain and types of SCD pain; (2) the Pain Assessment Tool; (3) SCD general knowledge and self-efficacy, (4) family cohesion, and (5) app usage. The primary outcome measure (knowledge acquisition for communicating about pain and types of pain) will be developed. Change in knowledge acquisition for communication relative to baseline was chosen as the primary outcome because Phase I participants strongly expressed that improving communication skills and understanding their pain were the primary reasons why teens would use the app. In addition to teens being recruited, their parent will also be recruited to complete a parent proxy version of the primary outcome measure.

3C5.1. Trial Design (n=100). A within-subjects (repeated measures) design will be used. A number of designs were considered. A comparative-effectiveness trial was rejected since there is no existing app geared for SCD teens that could act as an appropriate comparator. A randomized controlled design was contemplated, and we considered a number of possible control conditions (e.g., no treatment control, waitlist control, etc.). However, we rejected the RCT concept due to resource demands for obtaining a large sample size for sufficient power (i.e., time and cost relative to a 24-month Phase II timeline), and input from the EAB and parents. Specifically, the EAB and parents believe parents would not be interested in participating if the possibility of a control condition was present. The purpose of a Phase II grant is to continue the research and development efforts initiated in Phase I and prepare it for commercialization. Our primary goals are to fully build the app and assess for individual improvements in communication and pain identification over time. Thus, a within-subjects design was chosen. The advantages of the within-subjects design are increased power with smaller sample size, and a reduction in error variance associated with individual differences. While the lack of a control group is a limitation, it was necessitated to overcome challenges in recruiting SCD teens experienced in Phase I. We will devote project resources to recruiting and retaining a sample in the treated group (i.e., receives *Pinpoint* app)

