that is sufficient to detect pre-post changes in primary and secondary outcomes rather than spend resources on securing a sample of which half will not be treated. We will also avoid having parents decline to participate due to the chance their teen will not receive the app. We have included two design aspects to control threats to validity¹⁴⁴: (1) we have a 6-week interim measure to create a time-series on the assessment of change; and (2) we will include a measure of communication and knowledge related to influenza as a nonequivalent dependent variable, which we do not expect will change pre to post as a result of the app despite it being subject to the same history, maturation, or regression threats as our primary and secondary measures. We will also include demographics, especially age of the teen and parental age and education, as covariates in the analysis as statistical controls against threats such as maturation.

A description of the app was provided in **Sections 3C.1d** and **3C.4.3c**. Participants will download the app following the procedures outlined in **Section 3C.7.1**. Project staff will provide users with a one-on-one app orientation and how to use its unique features via videoconferencing. Daily notifications will engage users in daily app use and provide up-to-date information on users' progress. Participant responses will also be used to evaluate additional or on-going support of users' needs. To protect privacy and to ensure that the participant is the person completing the app activities, KB will uniquely identify the user's smartphone/tablet based off the device's "hardware footprint". The app will upload all app activity data to the KB secured web server database.

3C.6. Target Population. There are two populations: teens with SCD and their parent. Inclusion criteria for teens are: (a) age 13-17 years; (b) diagnosed with SCD; (c) own a smartphone or tablet, and (d) read and speak English. Parents will be recruited to complete a parent proxy version of the primary outcome measure (child's knowledge acquisition; see **3C.7.2**), but will not use the app. Parent inclusion criteria are: (a) parent/guardian of eligible child and (b) able to speak and read English.

3C.7. Trial Conduct.

3C.7.1. Recruitment and Visit Procedures.

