Recruitment and Screening: Potential study participants will be recruited through nationwide SCD support groups, SCD networks, social media ads, and existing research participant databases. Recruitment was a challenge during Phase I due to IRB delays at the study hospital. Thus, we reached out to multiple national organizations to assist with Phase I recruitment. During Phase I, a number of organizations expressed interest in being a recruitment center for Phase II. We have four committed organizations and four others have expressed commitment via phone or email communication (see **Letters of Support**). In addition, we have the commitment of the EAB and PAB to assist with recruitment.

Participants will be sent an email describing the study and a link to an eligibility screening survey via KB's secure server. The online screener will take 5 minutes. Phone screening will be used as needed. Participants will receive an email informing them of eligibility. Eligible participants will be scheduled for an orientation/baseline visit which will be conducted via videoconferencing; a reminder email and text message will be sent 3 days prior to the assessment (similar reminders will be sent for 6- and 12-week visits).

Orientation and baseline/pre-test assessment: In a one-on-one orientation session to be conducted via videoconferencing, participants will have the study explained and provide written consent (parent) and assent (child). Immediately following, the teen will complete pre-test surveys online using their personal smartphone or tablet device (see **3C.8**) which should take about 30 minutes to complete. Parents will complete an online survey (proxy measure of the primary outcome). After the surveys, teens will be assisted with app download, provided instructions on how to use the app, and encouraged to use the app daily.

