6-week interim assessment: Participants will complete interim assessments of initial changes (i.e., teens to complete all measures; parent to complete the single proxy measure assessing their child's knowledge acquisition). An invitation email and text messages containing a link to the surveys along with their unique password (PIN number) will be sent. Participants will complete the web-based surveys using either their tablet or smartphone; no video meeting will be required. Participants who do not complete the surveys within 3 days will receive an email and text reminder (and 3 more reminders at 3-day intervals if still not completed).

12-week post-test assessment: Participants will complete a post-test assessment via videoconference. They will meet individually with a study staff to complete the online surveys and a brief post-test interview.

3C.7.2. Outcomes: Baseline, Interim, and Post-test Measures. The baseline, 6-week interim, and 12-week post-test surveys will use a measure created by the investigative team and EAB as the primary outcome (i.e., knowledge acquisition for communicating about pain and types of pain). Secondary outcomes will be the app Pain Assessment Tool (PAT) and validated measures of SCD knowledge, disease self-efficacy, and family cohesion. Surveys should take 30 minutes to complete (see **Figure 7** and **Appendix E**).

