services. It is designed to assess SCD knowledge in seven areas: (1) pathophysiology, (2) genetics, (3) physical symptoms, (4) treatment, (5) self-care, (6) psychosocial and developmental issues, and (7) health care delivery. It has good psychometric properties.^{153,154} Higher scores represent greater knowledge.

Sickle Cell Self-efficacy Scale: This instrument, used to assess self-efficacy in adolescents with SCD,¹⁵⁵ is comprised of nine questions measuring participants' perceptions of their ability to function on a day-to-day basis and to manage SCD symptoms (e.g., pain). The instrument is reliable and valid for assessing adolescents' self-efficacy for engaging successfully in day-to-day activities despite having SCD.

Family Cohesion: Family cohesion will be assessed by the single item Family Cohesion scale from the Child Health Questionnaire (CHQ)¹⁵⁶, a pediatric quality of life (QOL) survey that has been normed for children age 5 to 18 years including those with chronic diseases. The CHQ consists of 28 items that assess 14 different concepts regarding child and family physical and psychosocial well-being. There is evidence of good reliability and validity of this measure¹⁵⁶ including the single-item Family Cohesion question.¹⁵⁷ This scale, which rates a family's ability to get along with one another, uses a single item ("In general, how would you rate your family's ability to get along with one another?") rated on a 5-point scale. The PAT is assessing QOL, therefore to reduce duplication of information and study burden only the Family Cohesion item will be administered.

CDC Flu IQ measure: This is a 10-item quiz developed by the Centers for Disease Control to assess general knowledge about influenza and vaccination. It will serve as a nonequivalent dependent variable.

App Usage: App use will be monitored using Web Trends software; tracking macro and micro level data. It will record how users move through the program including the time spent on each activity, response latency to individual items, and scores achieved on games. Summaries of these data (means, ranges) will be reviewed to understand usage patterns. Teens will be sent "push notifications" to encourage app use. Users will evaluate the app on the **System Usability Scale** at the 6- and 12-week assessment.¹⁴²

3C.7.3. Adherence, Dropouts, and Participant Compensation.

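### The covariates and the 6-week measure are credited with controlling threats to validity that they cannot remove from the mean change, and two sections disagree on whether baseline precedes app download

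*Combined protocol and SAP*

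**What the plan says.** Section 3C5.1 chooses a one-group repeated-measures design and is open about the price: "While the lack of a control group is a limitation". It then names two design features meant to control threats to validity. The first is the interim assessment: "we have a 6-week interim measure to create a time-series on the assessment of change". The second is "a measure of communication and knowledge related to influenza as a nonequivalent dependent variable". It adds teen age, parental age and education "as covariates in the analysis as statistical controls against threats such as maturation".

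Section C.10 and the closing part of the SAP return to the point: "Limitations of no control group are lessened via the use of a time-series design for outcome changes". Both sentences go on to name the nonequivalent dependent variable as the other mitigating feature. Neither mentions the covariates.

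The SAP tests within-person change over time and uses linear regression for the effects of age, sex and education; it does not name parental age. It runs the same analysis on the influenza quiz as a sensitivity analysis, and cautions that failing to find a change there does not prove there was none. Section 3C.7.2 describes that quiz as a 10-item instrument "to assess general knowledge about influenza and vaccination".

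On the order of events at the first visit, section 3C.7.1 has the pre-test first: "After the surveys, teens will be assisted with app download". Section 5B.1 puts download and instruction inside the orientation and the baseline assessment after it.

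**The concern.** The primary outcome is change from baseline, with the same questionnaires given three times in 12 weeks and no comparison group. Any average gain from growing older, from outside events or from repeated testing would look like benefit from the app. The plan tells the reader that certain features guard against this. If those features do not act on the mean change, the primary result supports a weaker statement about the app than the text implies.

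The baseline order matters for a related reason. There is one measurement before app use, and every change score depends on it. If some teens complete it after they have downloaded the app and been shown how it works, it is no longer cleanly a pre-app value.

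**Working it through.** **1. Baseline covariates and the mean change.** Let *c_i* be teen *i*'s 12-week change and *x_i* the baseline covariates. Fit *c_i = a + b′(x_i − x̄) + e_i* by least squares. The residuals sum to zero and the centred covariates sum to zero, so *a = c̄* exactly for complete data. The adjusted mean change is the raw mean change, whatever *b* is.

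A simulation agrees. It used N = 80, visit correlation 0.5, SD of change 1, no app effect, an assumed drift of 0.3, and covariates teen age, parental age and education, with 4,000 runs:

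| Drift | Raw mean change | Adjusted mean change | Rejection, raw / adjusted (0.05) |
|---|---|---|---|
| 0.3 for all teens | 0.301 | 0.301 | 74.9% / 74.5% |
| 0.3 on average, varying with age | 0.299 | 0.299 | 73.4% / 74.9% |

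**2. What the 6-week point can show.** Weeks 6 and 12 both follow app start. Take baseline mean μ:

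- drift only, 0.15 per six weeks: μ, μ + 0.15, μ + 0.30
- app effect only, 0.15 per six weeks: μ, μ + 0.15, μ + 0.30

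The profiles are identical. Without at least two pre-app points there is no pre-app trend to subtract. The 6-week point does show the time course. It also gives some information on regression to the mean, which would be expected mainly in the first interval. Section 5A.1 itself describes the design as pre-post.

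**3. The method, checked on the plan's own figures.** The SAP gives full inputs for one outcome, family cohesion: mean difference 6.51, SD 22.8, before-after correlation 0.5, alpha 0.0167. SD of change = 22.8 × √(2 × (1 − 0.5)) = 22.8, so the effect is 6.51 / 22.8 = 0.286. A two-sided paired t-test (noncentral t) needs N = 132 for 80% power and has 54.5% power at N = 80. The SAP states 132 and 54%, so both figures reproduce.

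**4. Illustrative size.** The documents give no drift estimate and no alpha for the primary outcome, so both are assumed; 0.0167 is the only level stated, for secondary outcomes. N = 80 is the SAP's figure after 20% dropout. With no app effect and drift δ in SDs of change, the noncentrality is δ√80; for example 0.2 × 8.944 = 1.789.

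| Assumed drift δ | δ√80 | Significant, two-sided 0.05 | Significant, 0.0167 |
|---|---|---|---|
| 0.05 | 0.447 | 7% | 3% |
| 0.1 | 0.894 | 14% | 7% |
| 0.2 | 1.789 | 42% | 26% |
| 0.3 | 2.683 | 76% | 60% |

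**5. Order of baseline and app download.**

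| Section | First | Then |
|---|---|---|
| 3C.7.1 | pre-test surveys | app download and instruction |
| 5B.1 | app download and instruction, within orientation | baseline assessment |

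These cannot both be followed. Section 3C5.1 refers the reader to 3C.7.1 for the download procedure.

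**6. Scope of the influenza measure.** Section 3C5.1 promises communication and knowledge; the instrument in 3C.7.2 covers knowledge only. The primary outcome includes communication, so that part has no nonequivalent counterpart.

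**The case against.** The strongest reply is that the limitation is already disclosed. Sections 3C5.1 and C.10 and the SAP all name the missing control group, and the last two say only that it is lessened, by the time series and the nonequivalent variable together. That stands: a reader might infer that the plan conceals the weakness of a single-arm design, and it does not. Partial help from the 6-week point is also compatible with that word. But 3C5.1 goes further, presenting the interim measure as controlling threats and the covariates as controlling maturation. The second claim is wrong for the analysis described, and the first is too strong. An age-at-visit term could in principle absorb some maturation, but the plan specifies none, and it would not touch history or retesting.

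A second reply is that every drift size is assumed, and that finding mean drift significant only shows that a test of mean change detects mean change. That also stands. A reader might infer from the table that a positive result would probably be drift; the documents do not support that. If maturation ran at 0.2 SD per year (an assumption), 12 weeks would bring 0.2 × 12/52 ≈ 0.05 SD, where rejection is 7%. History and retesting could add to this by an unknown amount.

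Third, a reader might infer that the baseline conflict inflates the result. Under the 5B.1 order, early learning would more likely raise the baseline score and shrink the measured change. The case for reconciling is that the baseline is not secure, whichever way the error runs.

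A reader might also suspect the 6-week setting, where "no video meeting will be required". Baseline and week 12 both use a videoconference and all surveys are completed online, so the 12-week change is not affected.

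**Conclusion.** The concern holds in a limited form. The covariate claim in section 3C5.1 is incorrect for baseline covariates in a one-group change analysis; this is algebra and needs no assumption beyond complete data. The 6-week point is over-credited in 3C5.1, C.10 and the SAP: it cannot separate steady drift from a steady app effect, though it partly informs regression to the mean. The influenza quiz is the only feature that can reveal shared drift. It is narrower than 3C5.1 promises, and no interval is stated for its change. The conflict between 3C.7.1 and 5B.1 is plain on the text.

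How much drift would matter cannot be fixed from the documents. The range of 7 to 76% at two-sided 0.05 (3 to 60% at 0.0167) rests on assumed drifts of 0.05 to 0.3 SD of change, N = 80 and no app effect, and serves as illustration only. The data remain usable; what must change is the attribution claimed for them. The sponsor should make the correction, but it does not undermine the choice of design.

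**What to change.** 1. Section 3C5.1: describe teen age, parental age and education as predictors of change, and remove the statement that they control maturation.
2. Section 3C5.1, section C.10 and the SAP's closing part: describe the 6-week measure as showing the time course after app start, with partial information on regression to the mean. Describe the primary result as uncontrolled change.
3. Reconcile section 5B.1 with section 3C.7.1, so that the pre-test is completed before app download and instruction.
4. SAP sensitivity analysis: report the mean 12-week change in the influenza score with a 95% CI, beside the primary change with its 95% CI. In 3C5.1, describe the influenza measure as covering knowledge only, to match 3C.7.2.

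The cost is wording and one extra summary on data already being collected, with no new participants, visits or instruments. The downside for the sponsor is a less favourable statement about how far improvement can be attributed to the app.

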There are 3 app modules with 8 activities in the Phase I prototype: (Module 1) **Learn About Communication** which includes (a) Body Scanner Reflection activity, (b) Self-Disclosure activity, and (c) Vocabulary Game; (Module 2) **Pain Assessment Tool** which includes (a) interactive Pain Survey and (b) Draw My Pain activity; and (Module 3) **Hope and Destiny Jr. content** which includes (a) Lifestyle Tips, (b) "Stories", and (c) Glossary. The Body Scanner Reflection is a guided meditation that segments the body into 6 sections and encourages

FIGURE 2: Pain Assessment Screen

[figure not shown]
reflection of how the user's body feels. The Vocabulary Game has users match as many SCD pain related words with their definitions in a 2-minute timed game. The Self-Disclosure Activity teaches the different types of communication levels using a Johari window and allows users to test their knowledge with example characters. The Pain Assessment Tool is an interactive survey containing 56 questions about user pain. The Pain Drawing Tool requires users to draw their pain on a full body diagram. Lifestyle Tips provide educational content to help prevent pain episodes. The "Stories" provide motivational excerpts from teens with SCD, and the Glossary is a list of medical terms and definitions.

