For evaluation period, participants will be sent an email describing the study and a link to a screening survey administered on KB's secure server that assesses inclusion criteria and demographic characteristics. The online screener will take about five minutes to complete. If needed, phone recruitment and screening will also be used. After being screened, participants will receive an email to inform them of their eligibility status. Eligible participants will be scheduled for an orientation and baseline assessment, which will be conducted via videoconferencing. Participants will have the study explained and provide online consent (parent) and assent (child). After providing consent and assent, participants will attend a one-on-one orientation. During the orientation, teens will be assisted with app download, provided instructions on how to use the app, and encouraged to use the app daily. Then the baseline assessment session will be conducted via videoconferencing. Participants will complete the (online) baseline survey(s) using their personal smartphone or tablet device, which should take about 30 minutes to complete.

Participants will complete a 6-week assessment of initial changes. An invitation email and text messages containing a link to the survey(s) along with their unique password (PIN number) will be sent. Participants will complete the online survey(s) using either their tablet or smartphone; no videoconferencing will be required for the 6-week assessment.

Participants will complete a 12-week post-test assessment. Participants will meet individually with study staff via videoconference to complete the online survey(s) and a brief post-test interview.

Consenting/Assent procedures are as follows:

A parent will be present and give consent for the child during the videoconference. Children will provide assent. Eligible children will be invited to participate, consented/assented using the following procedures:

1. Research staff will send an introductory email inviting eligible parents and children to participate and follow-up with emails and telephone calls to recruit them.
2. Interested parents will go to the study website to register and complete an online enrollment form, providing contact information (i.e., name, address, telephone numbers [home and mobile phones], and email address[es]) for themselves, their child, and people who can always locate them and their child (i.e., a locator).

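### Week 6 knowledge tests are taken unsupervised with the app's SCD content at hand, and no visit has a no-look-up rule, so measured gains may mix look-up with learning

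*Combined protocol and SAP*

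**What the plan says.** **Baseline.** Section 3C.7.1 describes a one-to-one video session in which "the teen will complete pre-test surveys online using their personal smartphone or tablet device", and the app comes next: "After the surveys, teens will be assisted with app download". Section 5B.1 gives the other order. It says "During the orientation, teens will be assisted with app download", and only afterwards "Then the baseline assessment session will be conducted via videoconferencing".

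**Week 6.** Teens complete all measures from an emailed or texted link: "Participants will complete the web-based surveys using either their tablet or smartphone; no video meeting will be required". The window is long: "Participants who do not complete the surveys within 3 days will receive an email and text reminder", and up to three more reminders follow at 3-day intervals.

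**Week 12.** Each teen completes the online surveys one-to-one with staff by videoconference (3C.7.1). Section 3C.8 says that post-tests are collected on the personal smartphone or tablet.

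**App content.** The Phase I app already has a game matching SCD pain words to definitions, and "the Glossary is a list of medical terms and definitions" (3C.1d). Phase II adds more book content and expands the communication module (3C.4.3c).

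**Tests.** Section 3C.7.2 lists the new primary measure of communication and pain knowledge, a 10-item SCD measure and a 25-item multiple-choice SCD measure. All three are scheduled at every assessment (Figure 7).

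**Logs.** Time on each activity is recorded (3C.7.2), and "Survey and app usage data will be linked" (3C.8). No analysis of app use during a survey is described.

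**The concern.** The primary outcome is knowledge, and the intervention supplies knowledge. A teen who answers the week 6 survey alone can open the app and read material on the topics being tested. That raises the score without learning, and the error can only favour the app.

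There is no control group to absorb this. Section 3C5.1 offers two design features against threats to validity: the 6-week measure and the influenza quiz. The first is the assessment most exposed to look-up. The second is meant to cover history, maturation and regression, and no influenza content is described for the app. In-app look-up would therefore lift SCD scores and leave influenza scores flat, which is the pattern the SAP treats as consistent with an intervention effect.

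**Working it through.** **Step 1. Conditions at each visit.**

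| Assessment | Staff on video | App downloaded | Rule against look-up |
|---|---|---|---|
| Baseline, per 3C.7.1 | Yes | Not yet | None |
| Baseline, per 5B.1 | Yes | Yes | None |
| Week 6 | No | Yes | None |
| Week 12 | Yes | Yes | None |

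Week 6 differs from baseline in supervision and, under 3C.7.1, in app access. Week 12 matches baseline in supervision and, under 3C.7.1, differs in app access. The documents set no time limit, app block or viewing of the teen's screen for any trial assessment.

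**Step 2. Check the frame against the plan's own figures.** The SAP gives a full set of inputs only for family cohesion: mean difference 6.51, SD 22.8, pre-post correlation 0.5, alpha 0.0167. It does not state sidedness.

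- SD of change = 22.8 × √(2 × (1 − 0.5)) = 22.8, so the standardised change is 6.51/22.8 = 0.286.
- A two-sided paired t-test then needs 132 for 80% power (SAP: 132) and has 54.5% power with 80 (SAP: 54%).
- 132/0.8 = 165 and 80/0.8 = 100, as stated.

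A two-sided paired t-test with 80 completers therefore reproduces the plan and is used below.

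**Step 3. What look-up alone could do.** Neither the share of teens who look answers up nor the gain from doing so is in the documents; both are assumed here. Let a share f gain g SD of the score, with no true learning. At correlation 0.5 the SD of change without look-up is 1 SD of the score.

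- Mean change = f × g
- SD of change = √(1 + f(1 − f)g²)
- Noncentrality = √80 × f × g / √(1 + f(1 − f)g²)

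Example, f = 0.2 and g = 1: 0.2/√1.16 = 0.186, and 0.186 × √80 = 1.66. Against critical t values (79 df) of 1.990 at alpha 0.05 and 2.445 at 0.0167, the chance of a significant improvement is 37% and 22%.

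Chance of a significant improvement from look-up alone, n = 80:

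| Assumed gain | Alpha | 10% look up | 20% | 30% |
|---|---|---|---|---|
| 0.5 SD | 0.05 | 6% | 14% | 25% |
| 0.5 SD | 0.0167 | 3% | 6% | 13% |
| 1 SD | 0.05 | 13% | 37% | 67% |
| 1 SD | 0.0167 | 6% | 22% | 50% |
| 1.5 SD | 0.05 | 23% | 62% | 91% |
| 1.5 SD | 0.0167 | 12% | 45% | 81% |

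With no look-up, the reference values are half of alpha: 2.5% and about 0.8%. The SAP applies 0.0167 to the secondary outcomes and states no alpha for the primary, so both levels are shown.

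On the 25-item test two looked-up answers are worth 2/25 = 8 percentage points. That cannot be turned into SD units, because the documents give no SD for the test.

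**The case against.** A reader might infer that the tests are closed-book at baseline and open-book at both follow-ups, with the app as the answer key. The documents do not support that reading, for four reasons.

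- **Baseline is not defined as closed-book.** Section 5B.1 puts the download before the baseline survey, and nothing bars a web search at baseline either.
- **Week 12 is attended.** The SAP's sample size counts teens with baseline and post-test results, and staff are on video at both. Look-up is less likely there, though not excluded, since nobody is told to view the screen or have the app closed.
- **The answer key is unproven.** The primary measure is still to be written, and its planned themes include trust, empathy and conflict management, which a glossary may not answer. App content is not mapped to the items of either SCD test. A teen may also take the survey on a different device from the one holding the app.
- **The influenza quiz is not blind to all look-up.** A teen who searches the web freely could raise that score too. It misses look-up confined to the app. The SAP itself warns that finding no difference does not prove there is none.

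These points narrow the concern. They leave standing an unsupervised week 6 assessment with app content at hand, no rule at any visit, and no check for concurrent use.

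**Conclusion.** The concern holds for week 6 and, more weakly, for week 12. Week 6 gains on the primary measure and both SCD knowledge tests cannot be read as learning alone, and the planned influenza comparison would not separate in-app look-up from an app effect.

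The size is not known. The table covers 3% to 91%, depending on the look-up share, the gain and alpha, and it assumes no true learning, which is the worst case. It shows that modest look-up could matter; it does not predict how much will occur. The figures should not be carried over to week 12, where supervision should lower the share.

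The plan should be changed, because the bias runs one way on the primary outcome and the remedy is cheap.

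**What to change.** 1. **Reconcile 3C.7.1 and 5B.1** so that the baseline surveys come before app download.
2. **Show one closed-book, no-look-up instruction** at all three assessments. At week 12, have staff ask the teen to close the app before starting.
3. **Optionally suspend the educational modules only** (communication and vocabulary, book content, glossary) while a survey session is active, with an automatic time-out. Without the time-out, a teen who opens the week 6 link and stalls could lose the intervention for days.
4. **In the SAP, use the linked activity-level logs** to flag surveys that overlap use of the educational modules, and repeat the primary and knowledge analyses without them. Do not count the Pain Assessment Tool or the journal: 3C.7.2 describes the former as an app tool, and it is itself due at weeks 6 and 12.
5. **State in the SAP that the main conclusion rests on the supervised baseline-to-week-12 contrast**, with week 6 as supporting information.

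The cost is one instruction screen, minor programming if item 3 is adopted, one sensitivity analysis on data already collected, and a short pause in educational content during a survey.
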